8.3. Adjustments for Covariates

No adjustments for covariates beyond potential inclusion of a baseline (IP baseline and QIV

baseline) for immunogenicity are planned.

8.4. Handling of Dropouts or Missing Data

Subjects who are withdrawn from the study will not be replaced. Missing data will be considered missing at random and no missing data will be imputed.

8.5. Interim Analyses and Data Monitoring

Safety data were reviewed by the safety review committee after Cohorts 1 and 2. There were no additional planned interim reviews or analyses.

Top line results (grouped by treatment) with no subject-level information were permitted by protocol. Any interim review will be reported in the CSR.

8.6. Multiple Comparisons / Multiplicity

There are no formal tests of hypotheses thus no adjustment for multiple tests. All p-values are descriptive only.

8.7. Examination of Subgroups

Due to the limited size of this study, there are no planned subgroup analyses. Exploratory analyses may examine primary or secondary endpoint results by age groupings, baseline titers or by QIV response, or those receiving Covid vaccine during the study.

9. PRIMARY OBJECTIVE: SAFETY EVALUATION (IPSS)

9.1. Extent of Exposure

IP exposure will be characterized as recorded on the eCRF. The protocol references actual dose, percentage of expected dose, and percentage of subjects receiving expected dose. The protocol also references vial weights. The eCRF captured only whether complete dose was administered. IP exposure will be reported as IP administered.

9.2. Adverse Events (AEs)

Adverse events were to be recorded from the day of informed consent through QIV Day 29. For subjects without QIV administration, follow-up for both AEs and SAEs was 28 days after IP. During the study treatment period subjectswere asked non-leading questions to determine the occurrence of spontaneously reported (unsolicited) AEs.

Symptoms were collected for the 7 days following IP administration using eDiaries, with clinical interpretation of data entries by the site investigator. At the discretion of the investigator, a symptom recorded by the subject on the eDiary may have been reported as an AE. The investigator was responsible for determining the severity and the relationship to IP for any eDiary-based AEs. There was no reconciliation of the database between the eDiary symptoms and other AE reports.

PE findings recorded as clinically significant, severe, or life threatening were to be recorded as AEs. Investigators usedtheir judgement regarding reporting of additional PE findings as AEs.

All AEs will be included in the listings. Only treatment emergent AEs will be summarized.

Separate listings of subjects who died, discontinued the study due to an AE, or experienced an SAE will be provided.

Treatment-emergent AEs (TEAE) are AEs with start dates between administration of the IP and IP Day29. If there is no administration of QIV then AE/SAE follow-up will be 28 days post IP administration. However, AEs with start dates past Day 29, if judged by the investigator to be IP-related, will be included in the treatment emergent set.

All AEs will be coded based on MedDRA (V24.0).

Where provided in Protocol Appendix 1, AEs will be graded according to the Vital Sign and Systemic Toxicity Assessments.

N (%) of subjects with at least one TEAE and N (%) of subjects with at least one treatment-related treatment-emergent AE (TRAE) will be summarized. TEAE and TRAE by worst severity will be summarized.

N (%) of subjects with TEAE will be reported by System Organ Class and Preferred Term (SOC/PT) and maximum severity. N (%) of subjects with TRAE will be reported by SOC/PT and maximum severity.

N (%) of subjects with TEAE by SOC/PT by overall frequency (decreasing) will be reported.N (%) of subjects with TRAE will be reported by SOC/PT by overall frequency (decreasing).

AEs will be reported by start date as: a) following IP administration, b) after IP administration and before QIV administration, c) within 7 days of IP administration, and d) after QIV administration.

No statistical test comparing adverse event rates will be done.

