2.2. Endpoints

2.2.1. Primary Endpoints

The primary endpoints are:

- The number and percentage of study participants who experience solicited local and systemic reactions during the 7 days after administration of investigational M2SR vaccine or placebo, as recorded through subject electronic diary (eDiary).
- The number and percentage of study participants who experience unsolicited AEs during the 28 days after administration of investigational M2SR vaccine or placebo and prior to administration of licensed QIV.
- The number and percentage of study participants who experience SAEs from the time of informed consent through 28 days after receipt of QIV.

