6.2.4.2. Systemic Events

During the reactogenicity reporting periods, subjects will be asked to assess headache, fatigue, myalgia, and illness. For the post-IP period, this will include recording the symptoms in the reactogenicity eDiary. The symptoms will be assessed by the subject as none, mild, moderate, severe or medically attended – emergency room visit or hospitalization was required according to the grading scale in Appendix 1.

If a Grade 3 or Grade 4 systemic event is reported in the reactogenicity eDiary after administration of IP, a telephone contact should occur to ascertain further details and determine whether a site visit is clinically indicated. If a systemic reaction persists beyond the end of the reactogenicity period following vaccine administration, the subject will be requested to report that information. The Investigator will enter this additional information as an AE in the eCRF. If a Grade 3 systemic reaction is reported after QIV administration (Visit 04) and prior to Visit 05, the site should ascertain whether a site visit is clinically indicated. If a Grade 3 or Grade 4 respiratory event (for example cough or wheezing) has been confirmed by the site, the subject should attend the clinic to provide a nasal swab that is tested as soon as possible for the full panel of respiratory agents.

Only an Investigator or medically qualified person is able to classify a subject's systemic event as Grade 4. If a participant experiences a confirmed Grade 4 systemic event, the Investigator must immediately notify the Sponsor.

Solicited systemic events following the IP dose include:

- Fever
- Chills
- Muscle aches
- Decreased activity
- Decreased appetite
- Headache
- Cough
- Sore throat

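### The SAP text specifies no summary of the primary unsolicited-AE endpoint, and its TEAE tables mix in eDiary symptoms and cover a different period

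*SAP*

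**What the plan says.** Protocol 2.2.1 lists solicited local and systemic reactions over 7 days, taken from the eDiary, as one primary endpoint. A separate one counts participants who "experience unsolicited AEs during the 28 days after administration of investigational M2SR vaccine or placebo" and before QIV.

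SAP 9.2 states that "Only treatment emergent AEs will be summarized" and defines the set by date: "Treatment-emergent AEs (TEAE) are AEs with start dates between administration of the IP and IP Day29". AEs starting after Day 29 are added if the investigator judges them IP-related. The planned summaries are any TEAE, any treatment-related TEAE, worst severity, and system organ class by preferred term. The same section then reports AEs in four start-date windows. None of these is split into solicited and unsolicited events. The word unsolicited appears once in the SAP, where it describes how events were collected.

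On diary symptoms, SAP 9.2 says that "a symptom recorded by the subject on the eDiary may have been reported as an AE" and that "There was no reconciliation of the database between the eDiary symptoms and other AE reports". SAP 9.2.1 tabulates the eDiary data separately.

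**The concern.** The study is descriptive, so the number and percentage of subjects is the whole result for this endpoint. If the TEAE tables are run as written, the figure a reader takes for the unsolicited-AE rate will contain solicited symptoms in some subjects and not in others, depending on how each investigator chose to report. One subject's headache could count under both primary endpoints, and another's only under the eDiary endpoint. The percentage would then be hard to compare across sites, age groups or other studies. If the vaccine causes more nasal or systemic symptoms than saline, some of that difference would reappear in the AE table as if it were a separate finding.

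**Working it through.** **The plan's own figure.** Protocol 1.4 puts the chance of seeing an AE of 20% prevalence among 15 subjects above 95%. This reproduces: 1 − 0.8^15 = 0.965. The present point does not depend on it.

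**Endpoint against planned summaries.**

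| | Endpoint (Protocol 2.2.1) | TEAE set (SAP 9.2) | Window after IP and before QIV (SAP 9.2) |
|---|---|---|---|
| Source | Unsolicited only | Any AE record | Any AE record |
| Start | IP | IP | IP |
| End | 28 days, and before QIV | Day 29, plus later IP-related AEs | QIV, whenever given |

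Neither summary matches. The window that ends at QIV is nearest, but Protocol 1.4 expects first IP doses in June 2021 and possibly no QIV until September. From 30 June to 1 September is already 63 days (31 in July, 31 in August, 1 more). In Cohort 3 QIV may be given up to day 42, which is 14 days past the endpoint's limit.

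**How diary symptoms reach the AE data.**
- Protocol 6.2.3: solicited as well as unsolicited symptoms are to be reported as AEs after investigator review.
- Protocol 6.2.4: eDiary data need no separate entry as AEs.
- Protocol 6.2.4.1 and 6.2.4.2: reactions that outlast the diary period are to be entered as AEs.
- SAP 9.2: re-reporting was at the investigator's discretion.

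The first, second and last statements conflict. The third is an instruction, so some diary symptoms are expected in the AE data on any reading.

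**Direction.** Every unsolicited AE in the endpoint window is also a TEAE, so the TEAE percentage cannot be lower than the endpoint percentage.

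**Size, on assumed rates only.** Let u be the unsolicited-AE rate and q the share of all subjects with a diary symptom reported as an AE, independent within subject. The any-TEAE rate is T = 1 − (1 − u)(1 − q).

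| u | q = 0 | q = 10% | q = 25% | q = 50% |
|---|---|---|---|---|
| 10% | 10% | 19% | 32.5% | 55% |
| 20% | 20% | 28% | 40% | 60% |
| 30% | 30% | 37% | 47.5% | 65% |

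**Between arms.** Take u = 20% in both arms, diary symptoms in 60% (active) and 30% (placebo), and the same fraction r of symptomatic subjects re-reported in each arm. The apparent difference is (1 − u) × r × (0.60 − 0.30) = 0.24r.

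| r | Active | Placebo | Difference (points) |
|---|---|---|---|
| 0 | 20.0% | 20.0% | 0 |
| 10% | 24.8% | 22.4% | 2.4 |
| 25% | 32.0% | 26.0% | 6 |
| 50% | 44.0% | 32.0% | 12 |
| 100% | 68.0% | 44.0% | 24 |

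The true difference in unsolicited AEs is zero in every row.

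**The case against.** The sponsor can say that the AE data are mainly the unsolicited stream. Protocol 6.2.4 does not require diary data to be entered again, and SAP 9.2 introduces AE collection as spontaneous reports obtained by non-leading questions. The diary has its own tables, and the start-date windows isolate the first 7 days. Protocol 8.3.2 itself plans TEAE summaries without a split, so the SAP follows the protocol. AE rates are not tested, the study is not powered for comparison, and randomisation in blocks of 3 within site roughly balances site habits between arms.

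Much of this stands. It makes the problem one of contamination of unknown size, and it places the gap in the protocol's analysis section as well as in the SAP. It does not produce the endpoint in Protocol 2.2.1. Balanced site habits also do not help if symptom rates differ between arms, as the last table shows.

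A reader might go further in three ways that the documents do not support.
- **That the endpoint is never tabulated.** Protocol 8 refers to table shells, which are not available here. The claim is limited to the SAP text.
- **That re-reporting merely adds equal noise to both arms and hides a difference.** Re-reported symptoms are reactogenicity and need not be equal, so they can also create a difference.
- **That fatigue and illness have no clear status.** Protocol 6.2.4.2 says "subjects will be asked to assess headache, fatigue, myalgia, and illness", but SAP 9.2.1 counts 7 systemic symptoms and 2 local reactions besides temperature. That is exactly the Appendix 1 list, which contains neither, and the SAP takes precedence.

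**Conclusion.** The point holds for the SAP text. A named primary endpoint has no specified summary, and the tables nearest to it differ from it in both source and period. The TEAE percentage will equal or exceed the endpoint percentage. The excess cannot be computed from the documents, because they give no AE rate, diary-symptom rate or re-reporting fraction. The 0 to 24 points is an illustration that rests on the assumed rates, on equal re-reporting in the two arms and on independence within subjects. If the same subjects tend to have both kinds of event, the excess is smaller. The secondary endpoint of unsolicited AEs after QIV does not have the same mixing of sources, since no eDiary was used then. The change should be made: it concerns a primary result and uses data already collected.

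**What to change.** In SAP 9.2, before database lock:

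1. Flag each AE as solicited-type or unsolicited. Solicited-type means an Appendix 1 symptom, or an upper respiratory infection diagnosis made up of such symptoms, with onset in the 7-day diary period. Reactions that persist past the diary are covered, because onset decides. The diagnosis clause is needed because Protocol 6.2.3 and 9.5 direct investigators to combine concurrent symptoms, and matching on single terms would miss those records.
2. Have grouped and unclear cases settled by reviewers blinded to treatment. SAP 1.1.2.3 gives the statistician and programmers the treatment codes throughout, so they should not make these calls.
3. Add a table of the number and percentage of subjects with at least one unsolicited AE with onset within 28 days of IP and before QIV, by treatment and age group.
4. Keep the all-TEAE tables as supportive.
5. Reconcile Protocol 6.2.3, Protocol 6.2.4 and SAP 9.2 on whether diary symptoms become AEs, and state which practice the sites followed.

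The cost is one derived flag, one table and a short blinded review, with no new data. Some headaches or coughs in the first 7 days that have nothing to do with the vaccine will be classed as solicited-type. The supportive TEAE tables will still show them.

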9. ADVERSE EVENT REPORTING

9.1. **Definitions**

Adverse Event

An AE is any untoward medical occurrence in a clinical study subject administered a medicinal (investigational or non-investigational) product. An AE does not necessarily have a causal relationship with the treatment. An AE can therefore be any unfavorable and unintended sign (including an abnormal finding), symptom, or disease temporally associated with the use of a medicinal (investigational or non-investigational) product, and whether related to that medicinal (investigational or non-investigational) product.

This includes any occurrence that is new in onset or aggravated in severity or frequency from the baseline condition, or abnormal result of diagnostic procedures, including clinical laboratory test abnormalities.

AEs will be monitored from the time of consent until Visit 03 (Day 28 after the IP dose administration) and from Visit 04 until Visit 05 (Day 28 after the QIV dose administration). SAEs or medically attended events will be documented from the time of consent until Visit 05.

Serious Adverse Event

An SAE is any untoward medical occurrence that meets any of the following conditions:

- results in death;
- is life-threatening, i.e., the subject was at risk of death at the time of the event (e.g., ventricular fibrillation and anaphylaxis). The term does not refer to an event which hypothetically might have caused death if it were more severe.
- requires inpatient hospitalization or prolongation of existing inpatient hospitalization:
 - Hospitalization refers to an overnight admission into hospital for the purpose of investigating and/or treating the AE. Hospitalization for an elective procedure, or routinely scheduled treatment for a pre-existing condition that has not worsened, is not an SAE.
- results in persistent or significant disability/incapacity, i.e., causing substantial disruption of the subject's ability to conduct normal life;
- is a congenital anomaly/birth defect;
- is medically significant, i.e., may not be immediately life-threatening or result in death or hospitalization but may jeopardize the subject's health or may require intervention to prevent one of the above outcomes. Examples of such events are intensive treatment in an emergency room or at home for allergic bronchospasm, blood dyscrasias, or convulsions that do not result in hospitalization or development of drug dependency or drug abuse.

Unlisted (Unexpected) Adverse Event

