9.2. Intensity of Adverse Events

All AEs will be assessed by the clinician using the grading system from FDA vaccine toxicity criteria (Appendix 2 for vital signs and systemic AE assessment; Appendix 4 for laboratory AE assessment). For events not included in the protocol-defined grading system, then the following guidelines will be used to quantify intensity.

Mild: events require minimal or no treatment and do not interfere with the subject's daily activities

Moderate: events result in a low level of inconvenience or concern with the therapeutic measures. Moderate events may cause some interference with functioning.

Severe: events interrupt a subject's usual daily activity and may require systemic drug therapy or other treatment. Severe events are usually incapacitating.

Life threatening: any adverse drug experience that places the subject or subject, in the view of the Investigator, at immediate risk of death from the reaction as it occurred, i.e., it does not include a reaction that had it occurred in a more severe form, might have caused death.

Changes in the severity of an AE should be documented to allow an assessment of the duration of the event at each level of intensity to be performed. Adverse events characterized as intermittent require documentation of onset and duration of each episode.

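### SAP 9.2 classifies adverse events by start date with no worsening clause, so an event that worsens after a dose within its original record is missed or credited to the wrong period

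*SAP*

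**What the plan says.** SAP 9.2 gives the working definition: "Treatment-emergent AEs (TEAE) are AEs with start dates between administration of the IP and IP Day29". There is one extension: "However, AEs with start dates past Day 29, if judged by the investigator to be IP-related, will be included in the treatment emergent set". On what reaches the tables it says: "All AEs will be included in the listings. Only treatment emergent AEs will be summarized". The treatment-emergent set then feeds the counts of subjects with any event and any related event, the worst-severity summaries, and the tables by system organ class and preferred term.

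The split into study periods also runs on start date: "AEs will be reported by start date as: a) following IP administration, b) after IP administration and before QIV administration". Two further displays follow, one for the 7 days after IP and one for after QIV.

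Protocol 9.1 takes a wider view of what an adverse event is. It includes any occurrence that is "new in onset or aggravated in severity or frequency from the baseline condition". Protocol 9.2 adds: "Changes in the severity of an AE should be documented". The stated purpose is to allow the time spent at each grade to be assessed. Protocol 8.3.2 uses the term treatment-emergent without defining it, and SAP section 1 says the SAP governs where the two documents differ. SAP 9.2 is therefore the only definition in force.

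**The concern.** SAP 9.2 has events recorded from consent, and the protocol's Table 2 places screening up to 28 days before dosing. Events that are already open when IP is given can therefore be in the database. Protocol 9.1 treats aggravation as an adverse event, but the SAP definition asks only when the record began.

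Unsolicited events in the 28 days after IP are a primary endpoint, and unsolicited events in the 28 days after QIV are a secondary endpoint. An event that was mild before a dose and severe after it is one that a safety table should show. If the rule removes such events from the tables, the error runs in one direction, towards fewer and milder post-dose events. For QIV there is also a question of attribution: a grade reached after QIV may appear in the post-IP table and not in the after-QIV display.

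**Working it through.** The plan gives no figure to reproduce here, so the check applies the SAP's wording to constructed records.

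**Rules applied**
- Treatment-emergent: start date from IP administration (Day 1) to Day 29, or start date after Day 29 and judged IP-related.
- After-QIV display: start date on or after QIV. I read this display as not limited to treatment-emergent events; otherwise most post-QIV events could not appear in it.
- QIV is assumed on Day 36, which is 36 − 1 = 35 days after IP and inside the 28 to 42 days allowed for Cohort 3.

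| Record | Start | Worsens | How worsening is entered | Treatment-emergent? | After-QIV display? |
|---|---|---|---|---|---|
| A | Day −5 | Day 3 | same record | No | No |
| B | Day 3 (same illness as A) | – | new record | Yes | No |
| C | Day 10 | after Day 36 | same record | Yes | No |
| D | Day 32, unrelated | Day 40 | same record | No | No |
| E | Day 40 | – | new record | No | Yes |

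**What follows**
- A and B are the same clinical course. One reaches the tables and the other only the listings, and the difference lies entirely in how the site entered it.
- Judging A to be related does not bring it in, because the relatedness extension covers only starts after Day 29.
- C stays in the post-IP tables. If maximum severity is taken over the whole record, its post-QIV grade is shown there, while the after-QIV display does not show the event at all.
- D is outside both. Whether it is collected is itself uncertain: protocol 9.1 has a gap in routine collection between Visits 03 and 04, whereas protocol 6.2.3 and SAP 9.2 do not.

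**Which way of recording do the documents point to?** Neither document says whether worsening opens a new record. Protocol 9.2 describes one event that passes through several grades, and it asks for a separate onset and duration only for intermittent events. That favours the single-record reading (A, C and D) without settling it.

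**How much do other displays recover?**
- eDiary tables (SAP 9.2.1) show the worst post-dose score whatever the pre-dose score. They cover only temperature and nine listed symptoms for 7 days after IP, use the IP evaluable set, and are not reconciled with event reports. There is no diary after QIV (protocol 8.3).
- Shift tables (SAP 9.4) cover vital signs only.
- Deaths, serious events and discontinuations due to an event are listed separately.
- Other unsolicited events have no second summary.

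**How close are the two periods?** SAP 8.2 notes that for about 40% of subjects the IP Day 29 and QIV Day 1 samples were taken on the same day. In those subjects an event still open at the end of the IP window runs straight into the QIV window.

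**The case against.** The strongest reply is that protocol 9.1 makes an aggravation an adverse event in its own right. If sites enter it that way, its start date is the date of aggravation and the SAP rule captures it. The eCRF completion guidelines may say so, and they are not among the documents. This stands, and it makes the loss conditional. It does not remove the need for a rule, because protocol 9.2 leans the other way and, without an instruction, sites may differ.

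The pool before IP is also narrow. The event must start between consent and dosing, still be open at dosing, and worsen in the same record. The screening list in protocol 6.1.2 names only medically attended and serious events, and exclusion 17 has people with minor illness enrolled after it resolves. This stands too.

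Four stronger readings are tempting, and the documents do not support them:
- *Worsening of chronic conditions in subjects aged 50 to 85 is lost.* Stable conditions are medical history, not events with a pre-dose start date. Their aggravation after dosing would be a new event under protocol 9.1.
- *An event that starts after IP and worsens after QIV vanishes from every post-dose summary.* If it starts by Day 29 it stays in the post-IP tables and is missing only from the after-QIV display.
- *Severe or related events disappear from the report.* All events are listed, and a solicited symptom such as nasal congestion would still show in the diary table.
- *The definition could hide events from the halting rules.* Those rules (protocol 7.3) act during the trial on reported events, and SAP 9.6 lists halting events without a treatment-emergent restriction.

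**Conclusion.** The point holds in a conditional form. SAP 9.2 has no worsening clause, either in its definition of treatment-emergent or in its period split. If worsening is kept in the original record, a pre-dose event that worsens after IP is listed but not summarized, and a pre-QIV event that worsens after QIV is absent from the after-QIV display, with its later grade possibly credited to IP.

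The number affected cannot be computed. It is the number of subjects, times the share with an event open at the dose, times the share of those that worsen in the same record, and the documents give neither share. Any percentage would be two unsupported assumptions multiplied together. It is probably small before IP. The pool at QIV could be larger, because it holds events from at least 28 days after IP.

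The conclusion rests on two assumptions: that at least some sites keep worsening in one record, and that the after-QIV display is built from start dates as written. The direction of error for the IP tables is towards a cleaner profile. That, and the low cost of repair, make the change worth making even for a small number of events.

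**What to change.** In SAP 9.2, define a treatment-emergent event as one that starts on or after IP administration, or that starts before it and increases in severity or frequency, or becomes serious, afterwards within the stated window. Keep the existing extension for late-starting related events. Use the date of worsening to place the event in a period and the maximum grade within that period for severity. Apply the matching rule to the after-QIV display, so that each grade is counted in the period in which it occurred.

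The alternative is to state that worsening is entered as a new event starting on the date of worsening. SAP 9.2 describes event collection in the past tense, so this option is sound only if the sites were in fact instructed to record that way. The eCRF completion guidelines should be checked first.

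The cost is a short change of wording, some programming, and slightly higher event counts. The programming depends on dated severity changes being in the database; protocol 9.2 requires that changes be documented but does not say where. If the dates are only in source documents, they would have to be retrieved for the events that were open at a dose.
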